# Matching of Exposed Participants to Unexposed Participants

The Safety Exposed Population will be matched with the Safety Unexposed Population. To minimise potential selection bias resulting from differences between these two populations, the PS method will be employed with the Inverse Probability of Treatment Weighting (IPTW) method, ensuring that both populations are balanced concerning crucial baseline variables.

For constructing the PS model, logistic regression will be used. This model will encompass essential baseline covariates (at index date), including age, gender, time since the last flare-up, and the total CAJIS score. Additional covariates may be included if deemed necessary. Balance diagnostics before and after applying weights will be reviewed to assess if there is any important residual imbalance. Standardised mean differences (SMDs) will be used to compare baseline covariates and estimated propensity scores between exposed and unexposed populations. SMDs greater than 0.1 for individual covariates on the weighted sample signify residual imbalance that may lead to biased results. A density plot of the estimated propensity scores by population will be generated to visually inspect the amount of overlap between the populations. A box plot of the propensity score weights for the unexposed population will also be generated to visually inspect for highly influential observations.

Other methods will be detailed in the SAP if needed.

The number and proportion of missing data for each baseline covariate to be included in the propensity score model will be reported for exposed and unexposed populations. The analysis

PAGE 66 OF 287

methods will proceed as a complete case analysis if, and only if, the proportion of participants in the unexposed participants with at least one missing value among variables required for the model is less than 5%. Otherwise, in addition to the complete case analysis, multiple imputation will be used as a sensitivity analysis to handle missing data. The methods to evaluate the effect of missingness and to handle missing data will be detailed in the SAP.

For participants who start palovarotene (or any investigational or commercialised FOP treatment) after being in the unexposed population, only their data until palovarotene intake with a minimum of 6 months of data collected will be included in the analysis.

The final report for key safety outcomes comparison between the exposed and unexposed populations will state the estimates and 95% CI and no hypothesis testing is intended to be performed.

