# 9.7.2 Sample Size Determination

The FOPal registry study aims to enrol a minimum of 67 participants with FOP treated with palovarotene and 33 participants with FOP not treated with palovarotene. Approximately half of the participants in each cohort (exposed and unexposed) will be paediatric (8 years to less than 18 years of age for girls and 10 years to less than 18 years of age for boys).

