# Comparison of key safety outcomes between the Safety Exposed and the Safety Unexposed Populations

The key secondary endpoints that will be descriptively compared between exposed and unexposed participants with FOP in the FOPal registry, include: 1) Annualised frequency of flare-ups categorised by overall occurrence; 2) Annualised linear height velocity and height z-scores until skeletal maturity or final adult height is reached; knee height may also be evaluated depending on data availability, and 3) Annualised frequency and descriptive characteristics of bone fractures, categorised by overall occurrence and location.

The index date (Day 1) corresponds to the initial administration of marketed palovarotene for the exposed participants (naïve and non-naïve), and to the ICF signed date for unexposed participants.

Participants in the Safety Unexposed Population will be followed from their index date until data extraction at the end of FOPal registry, or until start date of palovarotene, or any investigational or commercialised FOP first treatment intake, whichever comes first.

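### Propensity weights and the 0.1 SMD check are set on all ages, so age balance among the growing children who supply height velocity is neither ensured nor checked

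*Protocol*

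**What the plan says.** Section 9.7.3.4 (Matching of Exposed Participants to Unexposed Participants) states: "The Safety Exposed Population will be matched with the Safety Unexposed Population". It describes the propensity weighting as "ensuring that both populations are balanced concerning crucial baseline variables". Section 9.7.1 defines those populations by exposure alone, so adults are included. The weights come from a logistic propensity model on "essential baseline covariates (at index date), including age, gender, time since the last flare-up, and the total CAJIS score", with further covariates allowed. SMDs are used to "compare baseline covariates and estimated propensity scores between exposed and unexposed populations", and the reading rule is: "SMDs greater than 0.1 for individual covariates on the weighted sample signify residual imbalance that may lead to biased results".

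The second key comparison, set out in the same section, is "Annualised linear height velocity and height z-scores until skeletal maturity or final adult height is reached", with knee height if data allow. Under Growth Status, velocities and z-scores are derived only for growing children.

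On size, section 9.7.2 "aims to enrol a minimum of 67 participants with FOP treated with palovarotene and 33 participants with FOP not treated with palovarotene", and adds: "Approximately half of the participants in each cohort (exposed and unexposed) will be paediatric". Section 9.7.1 also defines paediatric exposed and unexposed populations. Section 9.7.3.5 uses them for Tanner stage; the matching text does not name them.

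**The concern.** Weights that balance a whole sample need not balance a part of it, and this outcome exists only in a part. Height velocity falls steeply with age through adolescence, so a modest age difference between exposed and unexposed children shows up as a growth difference. If exposed children are older, a harm appears that is not there. If they are younger, a real harm can be hidden. Growth is one of the three outcomes chosen for the exposed versus unexposed comparison, and the balance check as described is not looking where the problem would lie.

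An age gap confined to children is plausible. Section 7.3.1 reports premature physeal closure in 13 of 39 participants (33%) from 8/10 to under 14 years and in 0 of 38 from 14 to under 18. That could make prescribing depend on age among children in a way that does not apply to adults. This is an inference; the protocol does not say so.

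**Working it through.** The protocol gives no calculation to reproduce here: the 67 and 33 carry no precision target. The check is therefore analytic first, then by simulation.

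**Inputs from the protocol.** 67 exposed and 33 unexposed, about half children: 67 × 0.5 = 33.5 and 33 × 0.5 = 16.5, so about 34 v 17. This is an upper bound, because adolescents who have stopped growing supply no velocity. Covariates: age, gender, time since last flare-up, CAJIS. Flag: SMD above 0.1.

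**Assumptions not in the protocol.** Children aged about 9–18 with SD about 2.0 years; adults 18–61; overall age SD about 10.2 years; main-effects propensity model; no drug effect. Two growth curves: (A) 6 cm/year to age 11, falling to 0 at about 16.5; (B) 6 cm/year at age 9, falling 0.7 cm/year per year of age.

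**Step 1: what 0.1 means.** SMD = difference in means / SD. Overall: 0.1 × 10.2 ≈ 1.0 year. Children: 0.1 × 2.0 = 0.2 year.

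**Step 2: dilution before weighting.** With half children in each cohort, overall gap = 0.5 × child gap + 0.5 × adult gap.
- Child gap 0.8, adult gap 0: 0.4 / 10.2 = 0.04 overall; 0.8 / 2.0 = 0.40 in children.
- Child gap 1.5, adult gap 0: 0.75 / 10.2 = 0.07 overall; 1.5 / 2.0 = 0.75 in children. With an overall SD of 8 or 12 years the overall figure is 0.09 or 0.06.

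The all-ages SMD is under 0.1 in each case, even unweighted.

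**Step 3: after weighting, curve A, large sample.** With exposed children 0.8 years younger and equal adult ages, the weighted overall age SMD is 0.00, the weighted child SMD is −0.33 (unweighted −0.34), and the false velocity difference is +0.68 cm/year. At 67 v 33 the overall check passes in 93% of runs, with about +0.67 cm/year.

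**Step 4: after weighting, curve B, 67 v 33, 2,000 replicates, ATE weights.** Gaps are exposed minus unexposed, in years. The last three columns refer to replicates passing on all four covariates.

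| Child gap | Adult gap | All four covariates pass overall | Age SMD in children beyond ±0.1 | Mean child SMD | False velocity difference (cm/year) |
|---|---|---|---|---|---|
| +1.5 | 0 | 90% | 99% | 0.73 | −0.93 |
| +1.5 | −3 | 93% | 98% | 0.76 | −0.97 |
| +2 | −4 | 92% | 100% | 1.04 | −1.29 |
| −1.5 | +3 | 90% | 99% | −0.76 | +1.05 |

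ATT weights give similar false differences (−0.94 to −1.25, and +1.05), with all four covariates passing in 60–68% of replicates. At 6,700 v 3,300 the false difference remains, so it is not only small-sample noise.

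**Step 5: no systematic gap.** At 67 v 33, about 75% of replicates passing overall still exceed 0.1 in children. The error averages zero; its median absolute size is about 0.30 to 0.44 cm/year, depending on the curve and ages assumed.

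**Step 6: cases where the weights do help.** If exposure really is linear-logistic in age across all ages, the all-ages weights also balance children in large samples (child SMD −0.005). If exposed adults are 4 years younger as well, the child SMD moves part of the way, from −0.32 to −0.24.

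**The case against.** The strongest reply is that section 9.7.3 calls itself a summary and leaves technical detail to the SAP. Section 9.7.3.4 permits added covariates and other methods and refers to the appropriate safety populations, and section 9.7.4 plans subgroup analyses by age group. The functional form of age and outcome-specific weights are ordinary SAP content. That stands for the detail. It does not dispose of the point: the population, core covariates, diagnostic and threshold are already stated in the protocol for all ages, and none of these openings sets weights or a balance check in growing children. The stated check would give no signal that other methods were needed.

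The comparison is also descriptive, with estimates and 95% CIs and no tests. A biased estimate misleads all the same.

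Several stronger readings are tempting, and the documents do not support them:
- That the children **are** unbalanced for age. Imbalance is possible, not established; step 6 shows a case where it vanishes.
- That recruiting about half children makes overall age equal by design, so the weights leave the children's ages untouched. The protocol does not constrain adult ages, and the earlier treated and untreated groups in section 7.3.2 had median ages of 14 and 18. This reading holds only if adult ages happen to match.
- That an SMD under 0.1 is an acceptance rule. The text says diagnostics will be reviewed and treats values above 0.1 as a warning.
- That the 75% in step 5 is bias. It is chance imbalance with mean zero.

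**Conclusion.** The point holds in limited form. As written, the weights and balance check are set on all ages while height velocity comes only from growing children, so age balance in the children who matter is neither ensured nor checked. An overall age SMD under 0.1 can coexist with a material age difference among them, and that can create or mask a difference in height velocity or knee-height velocity. Height z-scores, being age-standardised, are much less affected.

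The mechanism needs only an age–exposure relation that differs between children and adults and a main-effects propensity model. The size does not follow from the documents: about 0.7 cm/year for a 0.8-year gap, and roughly 0.9 to 1.3 cm/year for gaps of 1.5 to 2 years, are illustrations resting on assumed gaps, age spreads and growth curves. The protocol should be changed, because the cost is small and growth is a named key safety outcome.

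**What to change.** In section 9.7.3.4, for the growth comparison (height velocity, z-scores, knee height), state that the weights will be derived to balance growing children. Either of two routes is sound: fit the propensity model within growing children of the Safety Exposed and Safety Unexposed Paediatric Populations, or add child and child-by-age terms to the full model. State also that SMDs, overlap and effective sample size will be reported in growing children. Keep the all-ages weights for flare-ups and fractures.

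For a 0.8-year gap at 67 v 33, either route cuts the mean false difference to about 0.01–0.02 cm/year. For gaps of 1.5 to 2 years, the within-children model brings it to about 0.06–0.17 cm/year in absolute size.

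The cost is one more model or a few added terms. At most about 34 v 17 children will support fewer covariates, and the interval may be wider. Residual imbalance will remain common: with the within-children model, the child SMD still exceeded 0.1 in about 30% of runs for a 0.8-year gap and in about 50–70% for gaps of 1.5 to 2 years. Balance in children must therefore be reported, not assumed, whichever route is taken.

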### 9.3.2.1 Demographic and Baseline Characteristics

The FOPal registry study will collect the following data at the Baseline Visit if available:

- Baseline demographics including date of birth, gender and race, where permitted;
- Reason for absence of treatment for unexposed participants, when available;
- Physical examination (only if clinic visit) including a general assessment as well as dermatologic, lymph nodes, HEENT, chest, cardiac, abdomen, limb/extremities, musculoskeletal, neurologic and other assessments (as per routine clinical care) for all participants at the Baseline Visit, at the first marketed palovarotene intake for exposed non-naïve participants and at the Follow-up/End of Study Visits;
- Medical or surgical history, excluding FOP-related history, within the 12 months before the signed informed consent date for exposed naïve or unexposed participants and within the past 12 months prior to the first marketed palovarotene intake for exposed non-naïve participants;
- FOP history including the date of symptom onset, date of diagnosis by a physician, method of diagnosis, date of genetic test if performed and type of FOP genetic variant;
- Number of flare-ups over the past 12 months prior to the first marketed palovarotene intake and until the signed informed consent date for exposed non-naïve participants or 12 months preceding the signed informed consent date for exposed naïve or unexposed participants;
- Movement mobility history within the 12 months before the signed informed consent date for exposed naïve or unexposed participants and over the past 12 months prior to the first marketed palovarotene intake and until the signed informed consent date for exposed non-naïve patients. The latter includes locations, mobility impact start date, change in movement, change in extra bone growth, symptoms if preceded by a flare-up event and causes.

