**PAGE 55 OF 287** 

#### 9.3.2.8 Effectiveness Variables

Cumulative Analogue Joint Involvement Scale

The CAJIS for FOP will be collected at the Baseline Visit and at the Follow-up/End of Study Visits (only if a clinic visit) if available.

The CAJIS is an objective measure of joint movement completed by the investigator to document total joint involvement [36]. This scale, which was developed by the investigators from the Center for Research in FOP and Related Disorders, assesses functional disability by categorising ROM across 12 joints (both right and left shoulder, elbow, wrist, hip, knee and ankle joints) and three body regions (cervical spine, thoracic/lumbar spine and jaw), with each joint/region assessed as: 0=normal (<10% deficit); 1=partially impaired (10% to 90% deficit); 2=functionally ankylosed (>90% deficit). The CAJIS total score is calculated as the sum of the scores of all joints/regions and ranges from 0 (no involvement) to 30 (maximally involved).

The examiner must also note and record (yes/no) if the participant:

- Can walk;
- Uses a wheelchair;
- Needs some help with activities of daily living;
- Needs complete help with activities of daily living.

Use of Assistive Devices and Adaptations for Daily Living

The use of assistive devices and adaptations for daily living will be collected at the Baseline Visit and at the Follow-up/End of Study Visits if available.

The questionnaire will be filled in by the participant or the proxy as per below table:

Questionnaire	If participant is an Adult (≥15 years)	If participant is a Child (<15 years) Filled by	
	Filled by		
	Participant	Participant	Proxy
FOP assistive devices assessment (Version 1.0)	X*		X

\* If participants are unable to answer on their own, an individual can be involved and reports only the participant's response on their behalf.

FOP=Fibrodysplasia Ossificans Progressiva.

In case of PRO completion by an individual (if participants are unable to answer on their own), the recommendations for such administration are detailed below:

- The individual should be different from a healthcare professional and should be the same across multiple assessments.
- The individual must only report the participant's response without any amendments or interpretation.

Assistive devices and adaptations for daily living (including healthcare utilisation) include:

- Mobility aids;
- Eating tools;
- Personal care tools;
- Bathroom aids and devices;
- Bedroom aids and devices;

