#### Flare-ups

At Baseline, the investigator will ask the participant how many flare-ups they experienced over the past 12 months. At each Follow-up Visit, the investigator will ask the participant how many flare-ups they experienced since the last visit.

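### The 5% missing-data trigger for the propensity-score analysis ignores the exposed cohort, and one named covariate, time since last flare-up, has no fully described data source

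*Protocol*

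**What the plan says.** Protocol 9.7.3.4 (Matching of Exposed Participants to Unexposed Participants) plans inverse probability of treatment weighting from a logistic propensity-score model. The model is to contain "essential baseline covariates (at index date), including age, gender, time since the last flare-up, and the total CAJIS score", and the list is left open: "Additional covariates may be included if deemed necessary".

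The preceding subsection sets the time origin. "The index date (Day 1) corresponds to the initial administration of marketed palovarotene for the exposed participants (naïve and non-naïve"); for the unexposed it is the date of consent.

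Missing covariate values are to be tabulated for both cohorts. The analysis then runs on complete cases alone exclusively when "the proportion of participants in the unexposed participants with at least one missing value among variables required for the model is less than 5" per cent. If that condition fails, multiple imputation is added as a sensitivity analysis beside the complete-case analysis. Further methods for missing data are left to the SAP.

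On the covariates themselves, section 9.3.2.8 says of flare-ups: "At Baseline, the investigator will ask the participant how many flare-ups they experienced over the past 12 months". At later visits the question is again how many, since the last visit. Section 9.3.2.1 lists, for non-naïve participants, "Number of flare-ups over the past 12 months prior to the first marketed palovarotene intake and until the signed informed consent date". The only related date belongs to the movement mobility history, which records "mobility impact start date, change in movement, change in extra bone growth, symptoms if preceded by a flare-up event and causes".

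**The concern.** Flare-ups, growth and fractures are the only outcomes that the protocol plans to compare between the cohorts, and all three comparisons rest on this one model.

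**Trigger.** The exposed cohort is where index-date covariates are plausibly thin. Participants may enrol after starting palovarotene, even before the registry opened in their country (section 9.1). For them the index date lies in the past. Their CAJIS at that date is a retrospective value (Table 3, footnote p; section 9.2.7.1), taken only if it was measured in routine care, because no assessment is mandated (section 9.2.6). The CAJIS text in section 9.3.2.8 does not list that time point: "The CAJIS for FOP will be collected at the Baseline Visit and at the Follow-up/End of Study Visits (only if a clinic visit"). Section 9.8.4 says that missing data are expected. A rule blind to this cohort can leave a selected set of well-documented exposed patients as the only basis for the comparison.

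**Covariate.** A variable called essential at index should be obtainable for every participant. If only counts are collected, the SAP cannot recover a date afterwards.

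**Working it through.** **Part 1: the trigger**

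Inputs: minimum enrolment of 67 exposed and 33 unexposed (sections 9.5 and 9.7.2); threshold of less than 5% with any missing covariate, unexposed only (section 9.7.3.4). The protocol gives no expected missingness rate and no number of non-naïve participants, so the rates below are assumptions. It has no figure of its own to reproduce.

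*Step 1, what 5% means for 33 people.* 1/33 = 3.0%, below 5%, so complete case alone. 2/33 = 6.1%, so imputation is added. One participant separates the two.

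*Step 2, how stable that is.* If each unexposed participant has a missing value with probability p, the chance that imputation is not triggered is P(X ≤ 1) = (1 − p)^33 + 33p(1 − p)^32.

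| Assumed p | P(not triggered) |
|---|---|
| 3% | 74% |
| 5% | 50% |
| 10% | 14% |
| 20% | 0.6% |

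*Step 3, what the rule permits in the exposed cohort.* Suppose 0 or 1 unexposed participant has a missing value, so complete case stands alone. Counts are rounded to whole participants, and overall missingness is out of 67 + 33 = 100.

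| Assumed exposed missingness | Missing | Complete cases of 67 | Overall missing |
|---|---|---|---|
| 10% | 7 | 60 | 7–8% |
| 20% | 13 | 54 | 13–14% |
| 30% | 20 | 47 | 20–21% |
| 50% | 34 | 33 | 34–35% |

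In every row the rule calls for complete case only.

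*Step 4, the same threshold applied to 67.* 3/67 = 4.5% passes and 4/67 = 6.0% does not. A trigger covering the exposed cohort would tolerate at most 3 participants with a missing value.

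**Part 2: the flare-up covariate**

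| Place in the protocol | What is recorded | Date of flare-up? |
|---|---|---|
| 9.3.2.8, Flare-ups | count over 12 months at Baseline; count since last visit later | no |
| 9.3.2.1 | count over 12 months before index or consent; up to consent for non-naïve | no |
| Tables 2 and 3, footnote l | count over 12 months | no |
| 9.2.7.3 and 9.2.7.4 | count since last visit | no |
| 9.3.2.1 and 9.3.2.8, mobility history and change | start date of each mobility impact, with any associated flare-up | no; dates the mobility change |

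Three cases follow:

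- The last flare-up came with a mobility change: the start date of that change can serve as an approximation.
- The last flare-up left no mobility change: it is counted but not dated.
- There was no flare-up in the look-back: time since the last one is undefined, known only to exceed the window.

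The two parts interact. If the last two cases are treated as missing, two of them among the unexposed trip the trigger, while any number among the exposed does not.

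**The case against.** The defence is substantial, and it limits the point in five ways.

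- A reader might infer that missingness is examined only in the unexposed, or that exposed patients vanish unnoticed. The text does not support this: missing values are reported for both cohorts, and only the decision rule is one-sided.
- A reader might infer that pubertal or skeletal status is wrongly left out of the growth comparison, since Tanner stage, bone age and epiphyseal status are collected. The covariate list is introduced as non-exhaustive, additions are expressly allowed, and further methods are deferred to the SAP. That is no error in this document.
- A reader might conclude that the flare-up covariate is not collected at all, or that the model cannot be fitted for many participants. Mobility start dates give a partial source, the eCRF is not available to check for a date field, and nothing in the protocol says how many participants would be affected.
- The trigger decides only whether a sensitivity analysis is added, because the complete-case analysis runs either way. Asking for multiple imputation as the main analysis would be a preference, not the correction of an error.
- The comparison is descriptive, with estimates and confidence intervals and no testing; 33 and 67 are minima; and the missingness rates above are assumed.

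All of this stands. It does not rescue the trigger, which is fixed in the protocol rather than left to the SAP. Nor does it give a described source for the date of a flare-up without mobility change.

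**Conclusion.** The point holds for two items.

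1. **The trigger is one-sided.** No level of missingness in the exposed cohort, reported or not, leads to the imputation analysis. With 33 unexposed it turns on a single person. At an assumed 30% missing in the exposed cohort, 20 of 67 would drop out and 47 would remain, and the rule would still call for complete case only if no more than one unexposed participant had a gap. The rule's structure is certain from the text. The size depends on the assumed rate and on enrolment at the minima.

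2. **Time since last flare-up is at best partly derivable** from the data described, and undefined for participants with no flare-up in the look-back. This carries medium confidence, because an eCRF date field cannot be excluded.

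The consequence is a possible selection effect and a poorly defined adjustment variable in the only planned between-cohort comparisons. It is worth correcting, but it does not touch the primary safety description of the exposed cohort.

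**What to change.** **Trigger.** Reword section 9.7.3.4 so that the imputation sensitivity analysis is added when 5% or more of participants in either cohort have a missing model covariate. At the minimum sizes this tolerates 1 of 33 unexposed and 3 of 67 exposed. The cost is one sentence, plus the imputation work when the condition is met.

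**Covariate.** Choose one of two routes.

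- Replace it with the number of flare-ups in the 12 months before index. This is not a pure wording change, because the count windows for non-naïve participants disagree: Table 3, footnote l, uses the 12 months before first marketed intake; section 9.3.2.1 extends the count to consent; section 9.3.2.8 asks about the past 12 months at Baseline, which lies wholly after index for anyone who started more than 12 months earlier. Reconcile them so that only pre-index flare-ups count. Also state how to treat unexposed children who only recently reached age 8 (girls) or 10 (boys), whose retrospective period is shortened (note to Table 4).
- Keep the covariate, add a field for the date of the last flare-up before index, and define the value for participants with none in the look-back. This costs one eCRF item and retrospective entry for those already enrolled. Data collection is planned to run to Q4 2035, so there is time.

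Align the CAJIS time points in section 9.3.2.8 with Table 3 and section 9.2.7.1 in the same amendment.
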